## 9. DATA ANALYSIS AND STATISTICAL CONSIDERATIONS

### 9.1. Hypotheses

The primary efficacy objective of this study is to assess the intracranial response (IR) rate in BRAF V600E mutation positive subjects assessed by Investigators using modified RECIST 1.1 criteria for Cohort A:

- Cohort A: 75 Subjects who are treatment-naive for brain metastases,

asymptomatic and stable on corticosteroids.

The study is designed to provide evidence to support the null hypothesis,  $H_0$ : IRR  $\leq$  35% or to reject it in favor of the alternative hypothesis,  $H_A$ : IRR  $\geq$  50% for BRAF V600E mutation-positive subjects in Cohort A.

The null hypothesis is based on results of BRF113929 (BREAK-MB), a study of dabrafenib in two cohorts of patients with histologically confirmed metastatic melanoma to the brain [Long, 2012]. The IR in patients with no prior local treatment for brain metastases was 39%; in patients with prior local treatment, the IR was 31%.

While the BREAK-MB trial demonstrated activity in patients with active brain metastases, all of the patients in that trial were asymptomatic from CNS disease. Vemurafenib, another elective inhibitor of oncogenic BRAF kinase that specifically targets cancer cells harboring mutated BRAFV600, was recently studied in a cohort of 24 patients with symptomatic brain metastases. Median PFS in the brain was 4.3 months and for other sites was 4.6 months. In addition, an improvement in performance status (decrease from baseline of at least 1 point of ECOG score) was seen in 83.3% of patients, and 66.7% reported a reduction of  $\geq$ 30% (compared with baseline dose) or complete discontinuation of corticosteroids.

This current trial is expected to build upon the current body of evidence of targeted therapy in melanoma brain metastases through an evaluation of the combination of dabrafenib and trametinib in patients with V600-mutation positive melanoma brain metastases.

The alternative hypothesis was selected as the IR that would be clinically relevant for this combination therapy. The study is designed to have 82% statistical power to detect an IR of 50% in V600E mutation-positive subjects who receive dabrafenib in combination with trametinib in Cohort A.

This hypothesis will be tested using a one-sided test for superiority with  $\alpha=0.05$ . There will be no other testing; therefore, there will be no adjustment of the Type I error for multiple testing.

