## 9.2. Study Design Considerations

### 9.2.1. Sample Size Assumptions

The sample size is based on the hypothesized improvement in intracranial response over study GSK BRF113929 (BREAK-MB) in Cohort A. 35% intracranial response (IR) is not clinically significant over existing therapies. An intracranial response (IR) of 50% is of clinical significance.

For the primary endpoint cohort (A), 75 BRAF V600E mutation positive subjects will be enrolled. At the time of the primary efficacy analysis, at least 33 subjects with an IR (44%) are required to establish that the evidence does not support the null hypothesis.

The sample size is based on a one-sided superiority trial of binomial proportions with an overall Type I error rate 0.05 incorporating an interim analysis with alpha-spending function proposed by Lan, 1983 with Pocock Boundary. The null hypothesis in Cohort A

will be tested assuming IR of 35% against an IR of 50% using a one-sided test for superiority with  $\alpha=0.05$  and power=82%. Sample Size Sensitivity

[Table 25](#) shows statistical power for the test of the null hypothesis in Cohort A under the assumed IR of 35% and for scenarios where the alternative response rate is lower and higher, assuming 75 BRAF V600E mutation positive subjects.

Table 25 Statistical Power Scenarios with 75 BRAF V600E Mutation Positive **Subjects in Cohort A**

IR	Statistical Power
40%	22.9%
45%	53.8%
50%	82.1%
55%	96.2%

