### **9.3.4. Interim Analysis**

There is a formal interim analysis for futility only with a statistical decision rule in this trial. For Cohort A, an interim analysis will take place after 22 subjects have been treated and had the opportunity for at least two disease assessments. The responses used in this interim analysis do not have to be confirmed. At least 8 of the 22 subjects must have an IR (intracranial CR or PR) for the trial to continue. If 7 or fewer subjects have an IR, this is evidence that the null hypothesis is true. If accrual is not complete at the time of the interim analysis, it will continue during this analysis.

An IDMC will review accumulating safety and efficacy data, including the results of the interim review of safety and efficacy and make recommendations to continue, modify, or terminate the study if there are concerns regarding safety. The IDMC will review the study results at least once for efficacy and futility. Additional routine reviews of safety data will be scheduled as needed. The IDMC responsibilities and review schedules are outlined in the IDMC Charter.

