### **9.3.5.1. Efficacy Analyses**

#### **9.3.5.1.1. Primary Analysis**

The IR is defined as the percentage of subjects who have a best confirmed intracranial complete or partial response by investigator assessment. Subjects who have an intracranial response of NE (not evaluable) or a missing response will be treated as non-responders, i.e., they will be included in the denominator when calculating the percentage. The primary efficacy analysis will be performed when all subjects in cohort A have had the opportunity for *three (3)* post baseline disease assessments. At least 33 of 75 V600E subjects (44%) must show an intracranial response for the null hypothesis to be rejected. The IR, along with exact two-sided 95% confidence interval, will be reported. Investigator-assessed IR will be considered the primary analysis.

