## 5. SAMPLE SIZE CONSIDERATIONS

### 5.1. Sample Size Assumptions

The sample size is based on the hypothesized improvement in intracranial response over study GSK BRF113929 (BREAK-MB) in Cohort A. A 35% intracranial response (IR) is not clinically significant over existing therapies. An intracranial response (IR) of 50% is of clinical significance.

For the primary endpoint cohort (A), 75 BRAF V600E mutation positive subjects will be enrolled. At the time of the primary efficacy analysis, at least 33 subjects with an IR (44%) are required to establish that the evidence does not support the null hypothesis. The sample size is based on a one-sided superiority test of binomial proportions with an overall Type I error rate 0.05 incorporating an interim analysis with the spending function proposed by Lan,(1983) with Pocock Boundary. The null hypothesis in Cohort A will be tested assuming IR of 35% against an IR of 50% using a one-sided test for superiority with  $\alpha=0.05$  and power=82%. There will be no other testing; therefore, there will be no adjustment of the Type I error for multiple testing and the primary endpoint test in the primary analysis will be performed at 5% level.

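### The sample-size text claims Pocock alpha spending for a futility-only interim, and the stated power and 5% error level are approximations that differ from the exact values of the count rule (type I error 6.0–6.7%)

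*Protocol*

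**What the plan says.** Protocol 9.2.1 sets Cohort A at 75 subjects ("75 BRAF V600E mutation positive subjects will be enrolled") and contrasts two rates: "35% intracranial response (IR) is not clinically significant over existing therapies", whereas "An intracranial response (IR) of 50% is of clinical significance". The test is one-sided with an overall type I error of 0.05, and the sample size is described as "incorporating an interim analysis with alpha-spending function proposed by Lan, 1983 with Pocock Boundary". SAP 5.1 has nearly the same words, "incorporating an interim analysis with the spending function proposed by Lan,(1983) with Pocock Boundary", but without calling it alpha spending, and adds that the primary test is made at the 5% level.

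The interim section reads differently: "There is a formal interim analysis for futility only with a statistical decision rule in this trial". Protocol 9.3.4 and SAP 4.1 continue the trial if at least 8 of the first 22 subjects respond, and the responses counted need not be confirmed. Both sections also have the IDMC look at the results at least once for efficacy as well as futility. At the final analysis, which counts confirmed responses, "At least 33 of 75 V600E subjects (44%) must show an intracranial response for the null hypothesis to be rejected" (Protocol 9.3.5.1.1).

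On power, Protocol 9.1 states: "The study is designed to have 82% statistical power to detect an IR of 50% in V600E mutation-positive subjects". The same 82% is stated in Protocol 3.1 and 9.2.1 and in SAP 5.1. Protocol Table 25 and SAP Table 1 give 22.9%, 53.8%, 82.1% and 96.2% at true rates of 40%, 45%, 50% and 55%. Neither document says how these were calculated.

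**The concern.** Spending alpha at an interim means that there is a boundary for declaring success there, and that the final test is made below the overall level. A futility-only look has neither feature. A reader of Protocol 9.2.1 and a reader of 9.3.4 would therefore describe two different designs.

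The second question is whether the stated power and error level belong to the rule that will be applied. With 75 binary outcomes and two whole-number cut-offs, both can be calculated exactly. If the exact type I error of the success rule is above 0.05, a result of exactly 33 of 75 would be declared significant at 5% by a rule that does not hold that level.

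**Working it through.** **Inputs.** Null rate 0.35, alternative 0.50, n = 75, one-sided 0.05 (Protocol 9.2.1); continue at 8 or more of 22 (Protocol 9.3.4, SAP 4.1); reject at 33 or more of 75 (Protocol 9.3.5.1.1).

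**1. Reproducing the plan's figures.** Assume a normal approximation with the null variance in the test, looks at 22 and 75, a binding futility stop and Pocock-type *beta* spending. Solving for a total beta that fits n = 75 gives 0.1796.

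- Beta spent at the interim: 0.1796 × ln(1 + (e − 1) × 22/75) = 0.0733. The futility limit is 7.60 of 22, so stop at 7 and continue at 8.
- Final critical value 1.597: 75 × 0.35 + 1.597 × √(75 × 0.35 × 0.65) = 26.25 + 1.597 × 4.131 = 32.85, so reject at 33.
- Power at 40/45/50/55%: 23.0/54.4/82.0/95.3%, against the stated 22.9/53.8/82.1/96.2%.

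Both cut-offs are recovered and every row is within 1 point.

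**2. The same with Pocock *alpha* spending and an efficacy stop (no futility stop).** Alpha spent at the interim is 0.05 × ln(1 + (e − 1) × 22/75) = 0.0204. The final critical value is 1.808: 26.25 + 1.808 × 4.131 = 33.72, so reject at 34, which is not the plan's 33. Power is 21.8/52.9/82.1/96.3%, also near Table 25. The table alone therefore does not show which method was used.

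**3. Exact values for the rule as given.** With the stop binding,

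P(reject | p) = Σ (x = 8 to 22) P[Bin(22, p) = x] × P[Bin(53, p) ≥ 33 − x].

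Ignoring the stop, it is P[Bin(75, p) ≥ 33].

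| True rate | Stated | Exact, stop binding | Exact, no stop | Stated minus exact with stop |
|---|---|---|---|---|
| 35% (type I error) | 5% | 6.02% | 6.68% | −1.0 |
| 40% | 22.9% | 25.3% | 27.6% | −2.4 |
| 45% | 53.8% | 57.3% | 61.3% | −3.5 |
| 50% | 82.1% | 83.9% | 87.6% | −1.8 |
| 55% | 96.2% | 95.9% | 97.9% | +0.3 |

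**4. Which column applies.** The binding-stop column uses one response count at both looks. The plan counts unconfirmed responses at the interim and confirmed ones at the end, so some subjects can help to pass the interim without counting later. That makes the interim easier to pass and moves the true values from the binding-stop column towards the no-stop column: 83.9% to 87.6% at a rate of 50%.

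**5. A cut-off that holds 0.05 exactly.** Replacing 33 by 34:

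| | Stop binding | No stop |
|---|---|---|
| Type I error (35%) | 3.81% | 4.14% |
| Power at 50% | 79.3% | 82.2% |

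**The case against.** The strongest reply is that the stated figures are a legitimate approximation. Step 1 recovers both cut-offs and comes within 1 point of every row, the documents never claim exact power, and the error at the design alternative is in the safe direction. SAP 5.1 speaks only of a spending function, which is compatible with beta spending. Recruitment to Cohort A was finished by Amendment 7, so no sample-size decision depends on the result. All of this stands, and it rules out several stronger readings.

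- A reader might infer that 82% and Table 25 belong to no rule in the plan. They do not match an exact calculation of the rule, but a normal-approximation design with the same two cut-offs comes close to them.
- A reader might infer that the trial is underpowered. For the 33/75 rule, exact power at 50% is above the stated figure.
- A reader might take the alpha-spending sentence literally and conclude that the final test must be tightened. With an efficacy cut at 13/22, holding 0.05 exactly would need 35/75, with power of 77.1% (74.8% with the futility stop). No efficacy boundary appears in either document, so those figures describe a different design.
- A reader might take the IDMC's efficacy review as an efficacy stop. A response-based futility rule requires the IDMC to see response data; the only interim rule given is 8/22.
- Amendments 6 and 7 changed 84% to 82% to agree with the SAP. The closeness of 83.9% to the superseded figure proves nothing, since no method is given for either.

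What the reply does not answer is the protocol's alpha-spending wording, or the error level. An approximation that yields a cut-off of 33 does not make that cut-off a 5% rule.

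**Conclusion.** Two things hold. First, the alpha-spending sentence in Protocol 9.2.1 conflicts with the futility-only interim and the full-level final test. It is a wording error and does not by itself make the power wrong. Second, the stated operating characteristics differ from the exact ones. Power is 1.8 points low at 50% and 2.4 and 3.5 points low at 40% and 45%, and 0.3 point high at 55%, measured against the binding-stop values. The type I error of 33/75 is 6.0% with the stop and 6.7% without it, against a stated 0.05. The error level is the more consequential of these.

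The figures assume independent responses with a common rate and exactly 75 subjects in the denominator. The range of 83.9–87.6% further assumes that every subject among the first 22 whose response is eventually confirmed already met the response criteria by the interim. A response that first appears after the interim would work the other way.

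**What to change.** In Protocol 9.2.1 and SAP 5.1, replace the spending sentence with: *one futility look at 22 subjects; no efficacy stop; no alpha spent*. In Protocol 9.3.4 and SAP 4.1, state that the IDMC's review of efficacy data carries no efficacy stopping boundary.

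Recompute the 82%, Protocol Table 25 and SAP Table 1 by exact binomial and name the method. For 33/75, give power at 50% as 83.9–87.6%, with the reason for the range, and report the type I error of 6.0–6.7% beside it.

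If 0.05 is to be held exactly, the success cut-off becomes 34/75. The type I error is then 3.8% with the stop or 4.1% without, and power at 50% must be restated as 79.3% or 82.2%. That choice should be recorded openly as a correction of the error level.

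The cost is a few sentences and one table in each document. The number of subjects and the conduct of the trial are unchanged; only the optional move to 34 alters the success criterion.

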## 9.2. Study Design Considerations

### 9.2.1. Sample Size Assumptions

The sample size is based on the hypothesized improvement in intracranial response over study GSK BRF113929 (BREAK-MB) in Cohort A. 35% intracranial response (IR) is not clinically significant over existing therapies. An intracranial response (IR) of 50% is of clinical significance.

For the primary endpoint cohort (A), 75 BRAF V600E mutation positive subjects will be enrolled. At the time of the primary efficacy analysis, at least 33 subjects with an IR (44%) are required to establish that the evidence does not support the null hypothesis.

The sample size is based on a one-sided superiority trial of binomial proportions with an overall Type I error rate 0.05 incorporating an interim analysis with alpha-spending function proposed by Lan, 1983 with Pocock Boundary. The null hypothesis in Cohort A

will be tested assuming IR of 35% against an IR of 50% using a one-sided test for superiority with  $\alpha=0.05$  and power=82%. Sample Size Sensitivity

[Table 25](#) shows statistical power for the test of the null hypothesis in Cohort A under the assumed IR of 35% and for scenarios where the alternative response rate is lower and higher, assuming 75 BRAF V600E mutation positive subjects.

Table 25 Statistical Power Scenarios with 75 BRAF V600E Mutation Positive **Subjects in Cohort A**

IR	Statistical Power
40%	22.9%
45%	53.8%
50%	82.1%
55%	96.2%

### 9.2.2. Sample Size Re-estimation

No formal sample size re-estimation is planned.

## 9.3. Data Analysis Considerations

### 9.3.1. Analysis Populations

All subjects who receive at least one dose of study medication will comprise the All Treated Subjects (ATS) population.

The V600E population will comprise all BRAF V600E mutation positive subjects who receive at least one dose of study treatment.

The V600D/K/R population will comprise all BRAF V600D/K/R mutation positive subjects who receive at least one dose of study treatment.

### 9.3.2. Analysis Data Sets

The primary datasets for efficacy will comprise efficacy data from subjects in the V600E population from Cohort A. The V600D/K/R population will also be used to report on secondary efficacy endpoints by cohorts.

The data sets for assessing all safety endpoints will include all safety data collected on subjects in the ATS population.

### **9.3.3. Treatment Comparisons**

Treatment comparisons are not applicable for this study. The primary objective will be supported by testing the null hypothesis in Cohort A. The four cohorts will not be compared statistically for any endpoint.

### **9.3.4. Interim Analysis**

There is a formal interim analysis for futility only with a statistical decision rule in this trial. For Cohort A, an interim analysis will take place after 22 subjects have been treated and had the opportunity for at least two disease assessments. The responses used in this interim analysis do not have to be confirmed. At least 8 of the 22 subjects must have an IR (intracranial CR or PR) for the trial to continue. If 7 or fewer subjects have an IR, this is evidence that the null hypothesis is true. If accrual is not complete at the time of the interim analysis, it will continue during this analysis.

An IDMC will review accumulating safety and efficacy data, including the results of the interim review of safety and efficacy and make recommendations to continue, modify, or terminate the study if there are concerns regarding safety. The IDMC will review the study results at least once for efficacy and futility. Additional routine reviews of safety data will be scheduled as needed. The IDMC responsibilities and review schedules are outlined in the IDMC Charter.

### **9.3.5. Key Elements of Analysis Plan**

Data will be listed and summarized according to the Novartis' reporting standards, where applicable. Complete details will be documented in the Reporting and Analysis Plan (RAP). Any deviations from, or additions to, the original analysis plan described in this protocol will be documented in the RAP and final study report.

As it is anticipated that accrual will be spread thinly across centres and summaries of data by centre would be unlikely to be informative, data from all participating centres will be pooled prior to analysis.

All data up to the time of study completion/withdrawal from the study will be included in analyses, regardless of duration of treatment.

The length of treatment for each subject will depend on the efficacy and toxicity of the treatment, so the duration of treatment and follow-up will vary among subjects. All available time-to-event data will be analyzed using appropriate statistical methods; subjects with shorter treatment and follow-up due to the natural history of their disease or medical necessities of the treatment of their disease will not be considered to have missing data. Consequently there will be no imputation for missing time-to-event data.

Demographic and baseline characteristics will be summarized according to current Novartis standards.

For the analysis of overall survival, the last date of known contact will be used for those subjects who have not died at the time of analysis; such subjects will be considered

censored.

For the analysis of PFS, if the subject received subsequent anti-cancer therapy prior to the date of documented progression or death, progression free-survival will be censored at the last adequate assessment (that is, the last assessment in which the visit level response is CR, PR, or SD) prior to the initiation of that anti-cancer therapy. Otherwise, if the subject does not have a documented date of progression or death, progression-free survival will be censored at the date of the last adequate assessment. Further details on rules for censoring will be provided in the RAP.

There will be no adjustments of the Type I error rate for multiplicity.

### **9.3.5.1. Efficacy Analyses**

#### **9.3.5.1.1. Primary Analysis**

The IR is defined as the percentage of subjects who have a best confirmed intracranial complete or partial response by investigator assessment. Subjects who have an intracranial response of NE (not evaluable) or a missing response will be treated as non-responders, i.e., they will be included in the denominator when calculating the percentage. The primary efficacy analysis will be performed when all subjects in cohort A have had the opportunity for *three (3)* post baseline disease assessments. At least 33 of 75 V600E subjects (44%) must show an intracranial response for the null hypothesis to be rejected. The IR, along with exact two-sided 95% confidence interval, will be reported. Investigator-assessed IR will be considered the primary analysis.

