### 4.1. Interim Analyses

There is a formal interim analysis for futility only with a statistical decision rule in this trial. For Cohort A, an interim analysis will take place after 22 subjects have been treated and had the opportunity for at least two disease assessments. The responses used in this interim analysis do not have to be confirmed. At least 8 of the 22 subjects must have an IR (intracranial CR or PR) for the trial to continue. If 7 or fewer subjects have an IR, this is evidence that the null hypothesis is true. If accrual is not complete at the time of the interim analysis, it will continue during this analysis.

An IDMC will review accumulating safety and efficacy data, including the results of the interim review of safety and efficacy and make recommendations to continue, modify, or terminate the study if there are concerns regarding safety. The specific responsibilities, review schedules and composition of the IDMC will be outlined in a separate document, the IDMC charter. The IDMC will review the study results at least once for efficacy and futility. Additional routine reviews of safety data will be scheduled as needed.

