### 5.2. Sample Size Sensitivity

Table 1 shows statistical power for the test of the null hypothesis in Cohort A under the assumed IR of 35%. It includes statistical power for scenarios where the alternative response rate is lower and higher. All statistical power calculations assume 75 BRAF V600E mutation positive subjects in the Cohort A All Treated Subjects population.

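### The 33-of-75 success rule does not hold the stated one-sided 5% type I error: its exact size is 6.0–6.7%, and 34 of 75 is the first count that holds it

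*Protocol*

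**What the plan says.** Protocol 9.2.1 describes a "one-sided superiority trial of binomial proportions with an overall Type I error rate 0.05 incorporating an interim analysis", with a null rate of 35%, an alternative of 50%, 75 subjects in Cohort A and 82% power. It cites Lan-DeMets alpha spending with a Pocock boundary. Protocol 9.3.5.1.1 turns this into a count: "At least 33 of 75 V600E subjects (44%) must show an intracranial response for the null hypothesis to be rejected". SAP 5.1 repeats the count ("at least 33 subjects with an IR (44%) are required to establish that the evidence does not support the null hypothesis") and adds that "the primary endpoint test in the primary analysis will be performed at 5% level".

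The interim rule is in Protocol 9.3.4: "At least 8 of the 22 subjects must have an IR (intracranial CR or PR) for the trial to continue". The same section adds: "The responses used in this interim analysis do not have to be confirmed". SAP 4.1 confirms the purpose: "There is a formal interim analysis for futility only with a statistical decision rule in this trial".

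Neither document names the final test, says whether the 5% is exact or approximate, or gives the attained size of the 33-of-75 rule. The word exact is applied only to confidence intervals.

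**The concern.** The plan gives two decision rules for its only hypothesis test, a count of 33 and a 5% significance level, and they can give different answers. With 75 subjects the binomial distribution is coarse, so one responder moves the size by more than two percentage points. A cut-off from a normal approximation can therefore land on the wrong side of 5%. Here the error favours false success: a result of exactly 33 would be declared positive by the count rule, while an exact 5% test would not reject. The planned exact 95% interval at 33/75 runs from 32.5% to 55.9%, so a positive claim would stand beside an interval that contains the null rate.

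**Working it through.** **Inputs.** p0 = 0.35, p1 = 0.50, n = 75, one-sided α = 0.05, reject at r = 33 (Protocol 9.2.1 and 9.3.5.1.1; SAP 5.1). Interim at 22 subjects, continue if 8 or more respond (Protocol 9.3.4; SAP 4.1).

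**1. Reproducing the plan's figures.** I used a normal-approximation group-sequential design with null-variance score statistic Z = (p̂ − p0)/√(p0(1 − p0)/n) and a binding futility look at 22/75. Pocock-type spending was applied to beta; that is my assumption, since a futility-only look spends no alpha. Results:
- Futility bound: 22 × (0.35 − 0.047 × √(0.2275/22)) = 7.6, so 8 of 22.
- Final bound: 75 × (0.35 + 1.597 × √(0.2275/75)) = 32.85, so 33 of 75.
- Power at 40/45/50/55%: 23.0/54.4/82.0/95.3%, against 22.9/53.8/82.1/96.2% in Protocol Table 25 and SAP Table 1.

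The match is close but not exact. The value 33 is plausibly a large-sample boundary that takes credit for the futility stop.

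**2. Exact size and power.**
- Ignoring the interim: P(X ≥ r), X ~ Bin(75, p).
- Stop binding on the same responses: Σ over x = 8 to 22 of P(X₁ = x) × P(X₂ ≥ r − x), with X₁ ~ Bin(22, p) and X₂ ~ Bin(53, p). The stop probability is 47.4% at p = 0.35 and 6.7% at p = 0.50.

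| True rate | r = 33, no stop | r = 33, stop | r = 34, no stop | r = 34, stop |
|---|---|---|---|---|
| 35% (size) | 6.68% | 6.02% | 4.14% | 3.81% |
| 40% | 27.6% | 25.3% | 20.4% | 19.0% |
| 45% | 61.3% | 57.3% | 52.2% | 49.4% |
| 50% | 87.6% | 83.9% | 82.2% | 79.3% |
| 55% | 97.9% | 95.9% | 96.4% | 94.6% |

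No column reproduces the plan's power table.

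**3. Unconfirmed responses at the interim.** The interim counts unconfirmed responses and the final test confirmed ones, so a binding stop removes less than the same-response calculation assumes. The documents give no rate for responses never confirmed. If 0/5/10/15% of subjects have one at the interim, the size at 33 is 6.02/6.38/6.56/6.64%. At 34 it is 3.81/3.99/4.08/4.12%, with power at 50% of 79.3/81.3/82.0/82.2%.

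**4. Ordinary single-stage tests**, one-sided p at p0 = 0.35:

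| Test | 33/75 | 34/75 |
|---|---|---|
| Exact binomial | 0.0668 | 0.0414 |
| Score, continuity-corrected | 0.0651 | 0.0396 |
| Wald | 0.0582 | 0.0361 |
| Mid-p | 0.0541 | 0.0329 |
| Score | 0.0511 | 0.0303 |

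All five miss 5% at 33 and meet it at 34.

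**5. The approximation with the stop binding.** A bivariate normal with correlation √(22/75) and cut-offs 8 and 33 gives 4.45% uncorrected. With continuity correction it gives 5.91%, close to the exact 6.02%.

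**6. When the decision changes.** Only at exactly 33 responders. Without and with the stop, that probability is 2.54% and 2.20% at a true rate of 35%, 9.25% and 8.02% at 44%, and 5.38% and 4.67% at 50%.

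**The case against.** The strongest reply is that the plan never promises exact control. Lan-DeMets spending is usually a large-sample method, and the 5% is described as overall, with the interim included. Tests that ignore the futility stop are then the wrong yardstick. Two methods that credit it do pass at 33: the uncorrected bivariate normal (4.45%) and a two-stage mid-p, (6.02% + 3.81%)/2 = 4.92%. On this view 33 is no slip, and the choice between approximate and conservative exact control is a matter of preference in a single-arm phase II trial.

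This explains where 33 probably came from, but it does not make the stated 5% correct. Neither document calls the level nominal or states the approximation. Continuity correction brings the approximation back to 5.91%, and the exact size exceeds 5% even with full credit for the stop. The cited alpha spending does not rescue 33 either: spending alpha on a Pocock-type efficacy look at 22/75 would put the final bound at 33.7, so 34.

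Three parts of the reply stand. The effect is confined to a single outcome. The power table has a plausible approximate source. Timing also matters: the SAP is dated March 2018 and its revision log says independent review has been done. The protocol's amendment rationale has the last Cohort A patient already 21 months on study, well past the third post-baseline scan at Week 16. A new threshold now could be a change made after the data were seen.

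**Conclusion.** The concern holds. As written, 33 of 75 carries an exact one-sided type I error of 6.0–6.7%, which is 1.0–1.7 percentage points above the declared 5%. The lower end assumes a binding stop on the same responses; the upper end ignores the stop. Counting unconfirmed responses at the interim places a binding-stop design between the two. The smallest count that holds 5% at either end is 34.

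The stated 82% power is not shown to be incompatible with 33, where exact power is 83.9–87.6%. The defect is in the size of the test and in the mismatch with SAP 5.1's 5%-level test. These figures assume 75 treated Cohort A subjects and independent responses.

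**What to change.** In Protocol 9.2.1 and 9.3.5.1.1 and SAP 5.1:

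1. Name the test: reject if the one-sided exact binomial p-value against 35% is at most 0.05.
2. With 75 treated subjects, state the threshold as 34 (45.3%), with exact size 3.8–4.1%.
3. Restate power at 50% as 79.3% with the stop binding on the same responses and 82.2% without it, noting that the true value lies between. Recompute Protocol Table 25 and SAP Table 1 by the same method.
4. Let the p-value rule govern if the treated number is not 75, since SAP 5.2 says "All statistical power calculations assume 75 BRAF V600E mutation positive subjects in the Cohort A All Treated Subjects population". The first single-stage exact count is 34 at N = 74 and 35 at N = 76 to 78. Carrying 44% forward fails: 33/74 has size 5.6% without and 5.1% with the stop; 34/77 has 6.0% and 5.5%.
5. Remove the Pocock alpha-spending wording or reconcile it with a futility-only interim.
6. Optionally report the exact two-sided 90% interval, whose lower limit matches the one-sided test: 34.2% at 33/75 and 35.5% at 34/75.

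The cost is one more responder and somewhat lower stated power. If the primary analysis has already been run, leave the prespecified count alone, report the exact one-sided p-value beside it, and document that the rule's exact size is 6.0–6.7%. That costs nothing in data. Keeping 33 before analysis is defensible only if that size is declared in place of 5%.
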